12.8 HANDLING OF MISSING DATA

For the primary outcomes using the full analysis set, last observation carried forward (LOCF) procedures may be used to impute missing data. A sensitivity analysis will be performed to evaluate the effect of assumption of imputation. For the secondary outcomes and safety analysis, missing data will not be imputed.

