6 INVESTIGATIONAL PLAN

6.1 STUDY DESIGN

[figure not shown]
This is a prospective, randomized, multicenter comparison study examining the outcomes of subjects with OA and knee pain undergoing a procedure to create a radiofrequency lesion of the genicular nerves with the CRFA system compared to subjects receiving HA. A total of approximately 168 subjects will be enrolled into this study, with subjects undergoing either CRFA or HA injection in a 1:1 randomization scheme. Follow up will be conducted for a total of 12-months post randomized procedure with the

Version #: 4.0

Version Date: 28Mar19

primary endpoint being completed at month 6. Subjects randomized to the comparison (HA) group will have the option to cross over to the neurotomy group after completing the 6-month endpoint assessment. They would then be followed for an additional 6 months. Pain, overall outcome, quality of life, pain medication use, and adverse events will be compared between the two treatment groups in order to determine success. Unless they have received an additional procedure on their index knee, subjects who were randomized to and received CRFA as their initial treatment will have the option to add 2 additional visits at 6-month intervals, representing 18 and 24 months post initial treatment.

CRFA = Genicular Neurotomy using Cooled Radiofrequency Ablation HA = Hyaluronic Acid Injection (Synvisc-One 6 mL injection)

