10.5 DISCONTINUATION / EARLY TERMINATION (ET)

Subjects may withdraw from the study at any time for any reason. Early terminations can occur under the following circumstances:

- 1. Subject withdraws consent.
- 2. Subject receives an additional procedure on their index knee.
- 3. Investigator withdraws the subject for any reason following discussion with the sponsor.
- 4. Investigator withdraws the subject immediately for emergent safety issues and reverts to institutional standards-of-care.

If it becomes necessary to exit the subject from the study early, the following exit procedures should be conducted if at all possible:

- (1) Obtain a Numeric Rating Scale for pain (subject completed questionnaire).
- (2) Obtain WOMAC Score (subject completed questionnaire).
- (3) Obtain an EQ-5D-5L Assessment (subject completed questionnaire).
- (4) Obtain a Global Perceived Effect Score (subject completed questionnaire).
- (5) Obtain Healthcare Utilization Form
- (6) Collect and assess Radiographs
- (7) Perform Physical Exam including BMI and vital signs
- (8) Perform Knee Exam
- (9) Perform adverse event assessment.
- (10) Assess concomitant medications.

The study may be terminated by the sponsor at any time for any reason. If a subject is withdrawn or the study is terminated, investigators will revert to institutional standards-of-care.

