10.6 Crossover visit (visit 5a)

Only subjects initially randomized to the control group (HA injection) who remain in **significant** pain at Visit 5 are eligible to receive crossover. Significant pain is defined as pain substantial enough to warrant receipt of a minimally invasive procedure (i.e., CRFA) per the investigators and subject assessment. Subjects do not need to formally requalify for the study to receive crossover per the inclusion/exclusion criteria; however, *confirmation and documentation is needed that subjects remain a medically appropriate candidate* for the CRFA procedure in order to be eligible.

Prior to receiving the Crossover procedure, the subject should be reminded of the risks of the CRFA procedure as described in section 4.6 and should sign the Crossover section of the informed consent document as noted in Section 8.2.

If the subject is still receiving relief from the HA injection at the time of this visit and/or is not medically appropriate for the CRFA procedure or elects not to Crossover, the subject should not receive crossover treatment and should continue to complete Visit 6.

It is anticipated that the Crossover procedure will occur on a different day than the 6 Month visit (Visit 5); however, it is allowable to perform the procedure on the same day if the Visit 5 items are completed first. Otherwise, the crossover treatment should occur within 30 days of Visit 5. If Visit 5A occurs on the same day as Visit 5, overlapping assessments noted below that were completed as part of Visit 5 do not need to be re-done (i.e., NRS, WOMAC, Healthcare Utilization, etc.).

If a subject choses crossover, the timing of their follow up visits (5B, 5C and 6) will now be based off their Visit 5A treatment date. Visit 5B/1 Month Visit should occur at post-operative day 30 ± 7 days. Visit 5C/3 Month Visit should occur at post-operative day 90 ± 14 days and the 6 Month Visit/Visit 6 should occur at post-operative day 180 ± 14 days.

At the Crossover Visit, the following assessments must be performed.

- (1) Verify Crossover consent was obtained
- (2) Verify and document that the subject remains medically appropriate for the procedure.
- (3) Obtain a Numeric Rating Scale for pain (subject completed questionnaire).
- (4) Obtain WOMAC Score (subject completed questionnaire).
- (5) Obtain an EQ-5D-5L Assessment (subject completed questionnaire).
- (6) Obtain a Global Perceived Effect Score (subject completed questionnaire).

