12.6.1 Primary Effectiveness Analysis

The primary efficacy parameter is the response rate which is defined as the proportion of subjects whose knee pain is reduced from baseline by ≥ 50% based on the NRS scale at 6 months after treatment.

Each subject's response to the treatment will be treated as an independent binomial event:

 H_0 : πc - πτ ≥ 0.05

Ha: $\pi_C - \pi_T < 0.05$

Where:

 Π_T : proportion of subjects with $\geq 50\%$ decrease from baseline in NRS pain score from baseline at the 6

months post randomization in the CRFA group

Πc: proportion of subjects with ≥ than 50% decrease from baseline in NRS score from Screening at the 6

months post randomization in the HA injection group

The non-inferiority margin is set at 5% for the primary efficacy parameter expressed as proportion. The difference of proportions between treatment groups will be calculated and a two sided 95% confidence interval will be constructed using Wald asymptotic confidence limits approach or exact binomial limits approach. If the upper bound is less than 0.05, then 'Non-inferiority' is established for the CRFA group relative to the HA injection group. If, in addition, the upper bound of the confidence interval is below zero,

the CRFA group can be determined to be 'Superior' to the HA injection group.

Treatment by study center interaction may be examined graphically across study center to determine the association between treatment and response rate is in the same direction or using logistic regression with response rate at 6 months as the response variable, and the study center, treatment group, study center

by treatment group interaction as predictor variables in the model.

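### Optional LOCF with no scoring rule for an additional index-knee procedure lets a subject who left for one count as a 6-month responder

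*Combined protocol and SAP*

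**What the plan says.** - **Endpoint.** Sections 6.2.1, 12.3.1 and 12.6.1 define response only as a reduction of at least 50% from baseline, "based on the NRS scale at 6 months after treatment". None mentions further treatment of the knee.
- **Exit.** Section 10.5 states that "Early terminations can occur under the following circumstances", and one item reads "Subject receives an additional procedure on their index knee". On exit, "the following exit procedures should be conducted if at all possible"; these include an NRS. The section does not say whether that NRS comes before or after the additional procedure.
- **Analysis set.** Section 12.2.2 keeps every randomized subject who was treated and has at least one effectiveness observation.
- **Missing data.** For the primary outcome, section 12.8 says that "last observation carried forward (LOCF) procedures may be used to impute missing data" and promises a sensitivity analysis on the imputation assumption, without naming a method. It adds: "For the secondary outcomes and safety analysis, missing data will not be imputed".
- **Extension.** Section 6.1 limits the 18- and 24-month visits: "Unless they have received an additional procedure on their index knee, subjects who were randomized to and received CRFA as their initial treatment" may continue. Section 8.2 states the same bar.
- **Data capture.** Footnote 4 to the schedule of assessments (section 9) places concurrent knee procedures within the adverse event assessment.
- **SAP.** Section 12 promises a stand-alone SAP. It is not among the documents.

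**The concern.** The protocol foresees an additional index-knee procedure, records it, and uses it to end participation and to bar entry to the extension. It never uses it to score response. Needing another procedure on the treated knee would ordinarily suggest that the assigned treatment had not given lasting relief. Under the written plan the same subject can be counted as a success.

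What is mainly at stake is each arm's absolute 6-month response rate. Section 4.5 gives reimbursement support as the study's primary rationale, so those rates are likely to be read on their own and not only as a difference. The choice also remains open until analysis, because LOCF is optional and no alternative is named.

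**Working it through.** **The plan's own figure.** Section 12.1 gives 134 evaluable subjects for 62% against 40%, margin 5 points, two-sided 5%, 90% power. The unpooled formula gives (1.960 + 1.282)² × (0.62×0.38 + 0.40×0.60) / 0.27² = 68.6 per arm, so 69 per arm and 138 in total. That is within 3% of 134; power at 67 per arm is 89.3%. Then 134/0.80 = 167.5, or 168 enrolled, which is 84 per arm. The point below does not depend on this figure.

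**How a responder can arise.** Take a subject with at least 50% relief at month 3 who has another procedure at month 4.
- If the subject exits, section 12.2.2 keeps the subject in the analysis. LOCF then carries forward the month-3 NRS, or the exit NRS, as a 6-month response.
- If the subject is not exited (termination only can occur), the 6-month NRS is taken after the procedure and counts as observed.

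**Size in one arm.** Let e be the number exiting for such a procedure, s the share of them carried forward as responders, and n = 84. Overstatement relative to non-response scoring = s × e/84. The documents give neither e nor s, so both are assumptions. For scale, 17 exits is about all of the planned 20% attrition in one arm (0.20 × 84 = 16.8).

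| Share s | e = 4 | e = 8 | e = 17 |
|---|---|---|---|
| 10% | 0.5 | 1.0 | 2.0 |
| 30% | 1.4 | 2.9 | 6.1 |
| 50% | 2.4 | 4.8 | 10.1 |
| 70% | 3.3 | 6.7 | 14.2 |

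(percentage points)

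**Effect on the difference.** Assume that 62% (CRFA) and 40% (HA) of subjects who stay respond; these are the planning rates of section 12.1.
- Non-response scoring: CRFA = 0.62 × (84 − e_T)/84; HA = 0.40 × (84 − e_C)/84.
- LOCF: add s × e/84 to each arm, here with s = 50%.
- Upper bound: Wald 95% limit for HA minus CRFA. Non-inferiority needs a bound below +5 points, superiority a bound below 0.

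Example with 10 CRFA and 0 HA exits under non-response scoring: CRFA = 0.62 × 74/84 = 54.6%; difference = 40.0 − 54.6 = −14.6; SE = √[(0.546×0.454 + 0.40×0.60)/84] = 7.62 points; bound = −14.62 + 1.96 × 7.62 = +0.3.

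| Exits CRFA / HA | Bound, non-response | Bound, LOCF |
|---|---|---|
| 4 / 2 | −5.2 | −6.4 |
| 8 / 4 | −3.2 | −5.6 |
| 8 / 17 | −9.6 | −4.0 |
| 10 / 0 | +0.3 | −5.8 |
| 13 / 4 | +0.6 | −4.8 |
| 15 / 8 | +0.1 | −4.1 |
| 16 / 0 | +4.8 | −4.9 |
| 17 / 0 | +5.5 | −4.7 |

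With 17 exits in each arm the difference is −17.5 points under both rules. For 0, 4 and 8 HA exits, superiority is first lost under non-response scoring at 10, 13 and 15 CRFA exits, which is 12% to 18% of that arm (10/84 to 15/84). Non-inferiority first fails at 17 CRFA and 0 HA exits.

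**The case against.** **The SAP may settle this.** Scoring of such events is normal SAP content, LOCF is only permitted, and a sensitivity analysis is promised. This stands in part: the finding concerns the protocol text, and the SAP may already contain a rule. But LOCF is the only method named, and a sensitivity analysis of imputation would not reach a post-procedure NRS that counts as observed. The Per-Protocol Set (section 12.2.3) removes major deviators; it does not score them.

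**Non-response is one choice among several.** Using the observed NRS regardless of later procedures is a recognised approach. That stands, so the rate is overstated only relative to non-response scoring.

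**The sizes rest on assumptions.** Subjects who seek another procedure may mostly be non-responders already, and LOCF carries non-response forward too. Entrants also agree to delay index-knee surgery (section 7.1, item 13). This stands, and is why the 10% share is shown.

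**Failing every later procedure could harm the HA arm.** The Synvisc-One labelling (Appendix 2) says that acute inflammation after injection may be managed with arthrocentesis or intra-articular steroids, and that benefit may still be apparent afterwards. A blanket rule could fail HA subjects who still have relief. This stands and shapes the fix.

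**Stronger readings that a reader might infer.**
- *The plan favours CRFA.* Not supported: with 8 CRFA and 17 HA exits, LOCF works against CRFA.
- *Subjects who exit would simply be dropped at 6 months.* This sits badly with section 12.2.2, which keeps them.
- *The later CRFA rates conceal exclusions.* The 18- and 24-month summaries are exploratory and cover one arm, the exclusion is stated in sections 6.1 and 8.2, and section 12.1.1 plans a disposition flow chart through 24 months. At 12 months, loss of terminated subjects is an inference from the absence of imputation. It does not apply to crossover subjects, who continue to Visit 6: "the timing of their follow up visits (5B, 5C and 6) will now be based off their Visit 5A treatment date".

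**Conclusion.** The gap is real and worth closing before the 6-month analysis. The written plan can count a subject who left for another index-knee procedure as a 6-month responder, and it can score a subject who stayed on pain measured after that procedure.

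On the assumed exit counts, the overstatement of an arm's rate runs from half a point (4 exits, 10% share) to about 10 points (17 exits, 50% share). Where the trial would fall cannot be known from the documents.

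The treatment difference changes only if exits or carried-forward shares differ between arms, and the direction is not predictable. A reader might infer that the primary conclusion is in danger. The scenarios do not support that at modest imbalances: with 8 CRFA and 4 HA exits, superiority holds under both rules. Losing it needs about 12% to 18% of CRFA subjects to have another procedure within 6 months under the combinations shown, which is an extreme case.

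**What to change.** In the SAP, before the 6-month analysis. These are scoring rules for analysis only and change no treatment or withdrawal decision.

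1. **Additional procedures.**
   - Do not let LOCF make a responder of a subject who exited for an additional index-knee procedure.
   - Score as a 6-month non-responder any subject who, after the assigned treatment and before the visit, had an additional index-knee procedure intended to treat persistent knee pain or OA. Fix the list of qualifying procedure types before the data are reviewed.
   - Do not count procedures that only manage a reaction to the assigned treatment (such as arthrocentesis), minor procedures before treatment (section 6.6.4), or the Visit 5A crossover.
   - Identify procedures from the concurrent knee procedure record.
   - Report two sensitivity analyses: one counting every additional procedure as non-response, and one using the observed NRS regardless of procedure.
2. **Other missing month-6 NRS values.** Replace optional LOCF with multiple imputation by arm from baseline, month-1 and month-3 NRS. Make the promised sensitivity analysis a tipping-point analysis.
3. **Later visits (a minor reporting addition).** Beside the observed-case CRFA rates at 12, 18 and 24 months, give the number of initially treated CRFA subjects excluded for an additional procedure or not followed.

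The cost is SAP wording, some programming, and agreement on the procedure list. The documents do not say that the indication for a procedure is recorded, so this must be checked. Reported response rates may be somewhat lower.

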13 ETHICAL, ADMINISTRATIVE, AND REGULATORY OBLIGATIONS

13.1 INDEPENDENT ETHICS COMMITTEE (IEC) OR INSTITUTIONAL REVIEW BOARD (IRB)

The study protocol, ICF document(s), subject recruitment materials, and any amendments must be submitted to and approved by the IRB/IEC prior to enrolling subjects. The IRB must be operating in compliance with 21CFR Part 56.

13.2 HEALTH INSURANCE PORTABILITY AND ACCOUNTABILITY ACT (HIPAA)

In accordance with the Health Insurance Portability and Accountability Act (HIPAA) of 1996, the Investigator must obtain authorization from the subject to use and/or disclose protected health information (PHI). HIPAA authorization may be obtained as part of the ICF or in a separate document. HIPAA authorization must include:

- A. Identification of the parties that can use and disclose the PHI
- B. Identification of the parties to whom the PHI may be disclosed
- C. A meaningful description of the PHI
- D. A description of each purpose for the use and disclosure
- E. Information about the subject's rights related to the authorization
- F. Information about the expiration of the authorization
- G. Instructions on how to revoke the authorization
- H. A statement about what may happen if the authorization is not signed
- A warning that once information has been released, it may be released again without further authorization

14 DATA AND QUALITY MANAGEMENT

All data obtained during this study will be entered into a 21 CFR 11 compliant Electronic Data Capture (EDC) system. All eCRF data must be supported by source documentation in the subject's medical/research record.

The sponsor will designate a qualified Monitor (CRA) to verify that study data are supported by adequate source documentation and are complete, accurate, and verifiable. Instances of inconsistent, missing or illogical data will be communicated to the Investigator or study coordinator and queried for resolution.

Site personnel will enter all data into the EDC system. The specific procedures for using the EDC system, including, but not limited to, entering and editing eCRF data and reviewing and resolving queries will be provided to investigative sites during training sessions and a training manual.

A Data Management Plan prepared by the sponsor will document the specifications for consistency and plausibility checks. Queries/corrections will be managed within the EDC system via the 'query process.' Prior to database lock, the Principal Investigator must electronically sign each eCRF.

15 RECORDS RETENTION AND ARCHIVAL

Study records must be maintained for a period of 2 years after the later of the following two dates: The date on which the investigation is terminated or completed, or the date that the records are no longer required for purposes of supporting a premarket approval application or a notice of completion of a product development protocol. Prior approval by the study sponsor is required before destroying or moving any study records off site.

After database lock, a CD or other electronic media containing a copy of the eCRF data will be provided to the investigator and must be maintained in the Trial Master File.

All source worksheets/documents, records, and reports must be retained by the study site in accordance with 21 CFR 812.140. All primary data or copies thereof (e.g., laboratory records, source documents, data sheets, correspondence, photographs, and computer records), which are a result of the original study observations, and are necessary for the reconstruction and evaluation of any study report, must be retained at the study site until otherwise notified by the Sponsor. Please contact Avanos Medical before archiving / destroying any study records.

16 MONITORING AND AUDITING

Avanos Medical will assign a qualified Monitor (CRA) to each site. The Monitor will visit the site at regular intervals throughout the study and at study completion to assess:

A. Compliance with applicable regulations and Good Clinical Practices

- B. Adherence to the study protocol
- C. Adequacy and accuracy of record keeping and source documentation
- D. Acceptability of storage of clinical trial materials and accountability of test articles
- E. Accuracy of eCRF data

Medical records for all subjects participating in the trial, eCRFs and study related documents (IRB approval, Instructions for use, correspondence pertaining to the trial, etc.) must be made available to monitor at each visit and upon request. The sponsor will create a Monitoring plan that outlines the anticipated schedule, processes, and expectations.

Avanos Medical, the IRB or regulatory authorities may also audit the study center to evaluate the conduct of the study. The clinical Investigator(s)/institutions(s) shall allow trial related monitoring, audits, IRB review and regulatory inspections by providing direct access to source worksheets/documents.

17 STUDY / SITE TERMINATION

Avanos Medical reserves the right to terminate the study or a study site at any time. Acceptable reasons for termination may include but are not limited to:

- Non-compliance with the Investigational Plan, Protocol, Regulatory Obligations, etc.
- Administrative Reasons

18 PUBLICATION PLAN

Avanos Medical will devise a plan for communications and publications regarding the study (primary, secondary, and extension objectives, sub analysis) and sub studies.

18.1 GENERALITIES

The publication policy described below applies for all publications related to this study.

- The agreement of Avanos Medical is mandatory before any submission made before the publication of any paper.
- Sub-investigators participating in the study may be listed on the paper at the discretion of the Steering Committee.
- Co-authors' order in the Authorship list will be submitted to each journal per journal-specific requirements; journal guidelines on the number of allowable authors will be followed.
- Avanos Medical must be cited in all publications where appropriate.

18.2 STEERING COMMITTEE

A Steering Committee will be established and will be responsible for assisting and guiding publication(s) of study results. The steering committee should consist of one or more clinicians qualified by experience.

The chair of the steering committee is the study Principal Investigator. If the study Principal Investigator leaves that role during the study, the steering committee will decide upon a replacement. A minimum of one Avanos Medical employee will facilitate the steering committee interaction. Members may be added or removed from the steering committee at any time as needs change or previously agreed to timelines get missed.

18.3 AUTHORSHIP CRITERIA

Authors for all publications should be qualified by experience and have participated in the clinical trial as an enrolling investigator or be a consultant responsible for key elements of the study process (e.g. protocol design, results interpretation, clinical strategy, etc.).

Lead Principal Investigator will be listed as the lead author, the Steering Committee will be represented, then authorship order will be determined by enrollment ranking pending journal allowances. Enrollment is defined as the number of patients who successfully reached the primary objective taking into account major data quality issues. A Working Group will be created which may allow for inclusion of participating investigators or referring sub-investigators who provided significant scientific contribution leading to the successful conduct of the trial.

